Design: We will include COPD subjects with a post-bronchodilator FEV1%predicted below 70% and chronic bronchitis. We will include subjects with at least 2 exacerbations in the last year to identify patients with significant burden due to chronic bronchitis. We will exclude subjects with recent respiratory events or procedures as we want to capture the benefit of HHHFA on chronic, stable COPD participants. Subjects who meet eligibility criteria will be randomized to HHHFA(intervention arm) or usual care (usual care arm). At baseline we will perform measurements in all subjects that include dyspnea, cough, health-related quality of life, and sleep quality questionnaires, spirometry, a 6-minute walk test, and chest CT. The HHHFA device will be provided to participants at the baseline visit.

Protocol: Heated, humidified high-flow air in Chronic Bronchitis

October 8, 2020

HHHFA V4.0

Subjects will use the device during sleep for 6 weeks and return for an end-of-study visit. At the follow-up visit (6 weeks), participants will repeat all baseline evaluations. At the follow-up visit, participants using the HHHFA will be asked whether they want to continue to participate in the sub-study. For participants that have consented to participate in the sub-study, they will use the HHHFA device for an additional 42 weeks. We will follow these participants who continue to use the HHHFA for 42 additional weeks (total 48 weeks) to assess for respiratory exacerbations.

We will compare changes in variables (e.g. FEV1 etc) over time in each treatment group. We will also compare changes in variables over time between groups. To evaluate the effect of treatment, we will use linear mixed effect models controlling for demographics and lung function.

II. Background

COPD is a leading cause of mortality in the U.S.[1] and worldwide[2] and is associated with high morbidity[3] and resource utilization[3], including costs due to clinic visits, chronic therapy, and frequent hospitalizations.[3, 4] COPD patients experience respiratory exacerbations defined as acute worsening of dyspnea, cough, and sputum production.[5]

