- Recent diagnosis (<2 weeks prior to study entry) of pneumonia, respiratory infection, COPD exacerbation, or acute bronchitis requiring antibiotics and new/increased dose of systemic corticosteroids
- Thoracic surgery or another procedure in the last six months that may result in instability of pulmonary status
- Recent medical or surgical history of upper airway disease that may interfere with intervention (e.g., sinus surgery, significant nasal polyps)
- Recent chest illness (trauma, pneumothorax etc).
- Basal skull surgery in the last 6 months
- Open skin ulcer or rash where the nasal cannula will be worn
- Tracheostomy or laryngectomy
- Pregnancy

XI. Schedule of events

After obtaining informed consent, participants will perform a screening pre-bronchodilator and post-bronchodilator spirometry using the EasyOne Spirometer (Zurich, Switzerland) according to American Thoracic Society-European Respiratory Society standards. Participants who meet eligibility criteria will be randomized (2:1) to receive either HHHFA or usual care for 6 weeks. Randomization will be performed using sealed envelopes.

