Baseline visit. After randomization, participants will have baseline measurements and training in the device. Participants will provide information regarding demographics, medical history, COPD history including prior exacerbations, hospitalizations, and pertinent medication use. Weight, height, and vitals will be recorded. Participants will complete Medical Research Council dyspnea scale (MRC),[45] St. George's Respiratory Questionnaire (SGRQ),[46-48] COPD Assessment Test (CAT),[49], Pittsburgh Sleep Quality Index (PSQI),[50], and Cough and Sputum Assessment Questionnaire (CASA-Q).[51] Subsequently, participants will perform a 6-minute walk test follow by an inspiratory and expiratory chest CT. Chest CT will be performed based on quantitative CT lung protocols.[52] TLC and residual volume (RV) will be measured at maximal inspiration and maximal expiration, respectively. We will quantify % emphysema and % gas trapping based on chest CT images. Quantified % emphysema will be defined as the percentage of voxels less than -950 Hounsfield units at TLC. Quantified % gas trapping will be measured at TLC as the percentage of voxels less than -856 Hounsfield units at RV. A parametric response map (PRM) will be constructed to reduce the misclassification of emphysema as gas trapping. Voxels with emphysema on TLC will be eliminated from the voxel count of gas-trapped areas after image matching of TLC and RV images. Airway geometry including Pi10, wall thickness, and visual mucus plugs will also be assessed.[52, 53] Lastly, subjects will receive training and the HHHFA with information materials and a study personnel contact number.

Phone Call at Week 1. Three to seven days after enrollment, a member of the research team will contact the participant to address any concerns or questions regarding the device (device training) and/or the study, and adverse events.

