Follow-up visit (6-weeks). After 6 weeks, participants will return to the CRU with the HHHFA device and perform the same procedures in the same order as at the baseline visit including weight, height, vitals, spirometry, MRC questionnaire, CAT questionnaire, PSQI questionnaire, CASA-Q questionnaire, 6-min walk test, inspiratory and expiratory chest CT. Information regarding changes in medication usage including frequency of rescue inhaler, exacerbation and hospitalizations since the last visit will also be collected. Participants in the HHHFA arm will be asked whether they want to continue to participate in the sub-study that will have them use the HHHFA for an additional 42 weeks. Participants that are not interested in participating in the sub-study, will return the device at the 6 week follow-up visit. Participants interested in participating in the sub-study can ship the device to the research team following their completion of the sub-study that will end at 48-weeks.

Phone Call visit at 12-weeks Only participants in the HHHFA sub-study group will receive a phone call at 12 weeks. Assessment for respiratory exacerbations will be performed.

Protocol: Heated, humidified high-flow air in Chronic Bronchitis

October 8, 2020

HHHFA V4.0

Phone Call visit at 24-weeks. Only participants in the HHHFA sub-study group will receive a phone call at 24 weeks. Assessment for respiratory exacerbations will be performed.

Phone Call visit at 36-weeks. Only participants in the HHHFA sub-study group will receive a phone call at 36 weeks. Assessment for respiratory exacerbations will be performed.

Phone Call visit at 48-weeks. Only participants in the HHHFA sub-study group will receive a phone call at 48 weeks. Assessment for respiratory exacerbations will be performed. Patients will ship the HHHFA device back to the company.

Table 1. Schedule of events summary

[figure not shown]
Activity	Visit 1	Phone Call visit (week 1)	Follow-up visit (6-weeks)	Phone Call visit (12-weeks)	Phone Call visit (24-weeks)	Phone Call visit (36-weeks)	Phone Call visit (48-weeks)
Informed Consent	X						
Screening evaluation and enrollment	X						
Spirometry	X		X				
Demographics and medical history	X		X				
Respiratory condition-related medications only	X		X				
Modified physical exam	X		X				
SaO ₂ at rest	X		X				
Randomization	X						
HHHFA device training and support	X	X	X	X	X	X	X
MRC questionnaire	X		X				
SGRQ Questionnaire	X		X				
CAT score	X		X				
PSQI	X		X				
CASA-Q	X		X				

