6-MWT	X		X				
Chest CT	X		X				
Respiratory exacerbation assessment	X	X	X	X	X	X	X
Adverse events	X	X	X	X	X	X	X
HHHFA Return device			X	X	X	X	X

Protocol: Heated, humidified high-flow air in Chronic Bronchitis

October 8, 2020

HHHFA V4.0

Protocol Summary

XII. Study procedures

Vitals, Height and Weight

The subject will have vitals taken by a CRU nurse: Height, weight, blood pressure, SaO₂ (saturation of oxygen in the blood), heart rate, temperature, and breathing rate. This will take approximately 20 minutes.

Six-min walk test

The test measures the distance a patient can walk on a flat, hard surface in six minutes.

Urine Pregnancy Test

Women of childbearing potential will have a urine pregnancy test as well. Before beginning the CT and MRI scans, the urine pregnancy test for females of childbearing potential will be checked. If the result is positive for pregnancy subject will be withdrawn.

Spirometry

The subject's FEV₁, FVC and the FEV₁/FVC ratio will be determined after three acceptable spirometry efforts are obtained. After prebronchodilator spirometric manoeuvres, two puffs of albuterol metered dose inhaler were administered using a spacer. Postbronchodilator manoeuvres were performed between 15 and 20 min.

CT Scans

The subject will be then taken to the Research CT Imaging Suite for their CT scan. A CT scan combines a series of X-ray images taken from different angles and uses computer processing to create cross-sectional images of the lungs. The CT scan will provide more detailed information than a standard x-ray. Once in the CT lab, the subject will be asked to remove any metallic items from their person (jewelry, piercings that can be removed easily, etc.). If the items to be removed involve clothing, the subject will be allowed to change in a

private restroom within the CT Suite and will be given a hospital scrub top to wear. We will explain the scanning procedures again to the subject and they will be reminded that they may ask questions at any time during the procedure(s). The subject will then be placed on the movable exam table of the CT scanner.

Three scans will be done in the CT scanner. One scout scan will be done to position the subject and then a total of two non-contrast CT scans will be done: Total Lung Capacity (TLC) and Residual Volume (RV).

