## **Cover Page for Statistical Analysis Plan**

Sponsor-Investigator:	[name]
NCT Number:	NCT03959982
Unique Protocol ID:	201905817
Official Title:	The Effect of Heated, Humidified High-flow Air in COPD Patients With Chronic Bronchitis
Date of Document:	01 July 2019

Assessment of the effectiveness of the intervention by assessing the change in the PSQI, CAT, and the 6-minute walk from enrollment to the 6-week visit. The Wilcoxon rank-sum test will be used to compare changes in PSQI, CAT, and the 6-minute walk test from enrollment to the 6-week visit between the intervention and the control group. The Wilcoxon rank-sum test will be used because the dependent variables will most likely not follow normal distribution.

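### Baseline PSQI, the other questionnaires, the 6-minute walk and CT are taken after randomisation with no masking described, so knowledge of the arm may bias the change scores

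*Protocol*

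**What the plan says.** The Protocol's XI. Schedule of events gives the order of Visit 1. Consent and screening spirometry come first. Then: "Participants who meet eligibility criteria will be randomized (2:1) to receive either HHHFA or usual care for 6 weeks", using sealed envelopes. The Baseline visit paragraph continues: "After randomization, participants will have baseline measurements and training in the device". It lists demographics, history, medication and vitals, then MRC, SGRQ, CAT, "Pittsburgh Sleep Quality Index (PSQI),[50], and Cough and Sputum Assessment Questionnaire (CASA-Q).[51", followed by the 6-minute walk and the chest CT. The visit closes with handover: "Lastly, subjects will receive training and the HHHFA with information materials and a study personnel contact number".

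The Design paragraph of I. Introduction describes randomisation first and then says "At baseline we will perform measurements in all subjects that include dyspnea, cough, health-related quality of life, and sleep quality questionnaires". Only the order of its sentences bears on timing.

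Table 1 places all of this at Visit 1. The randomisation row and the "HHHFA device training and support" row stand above the questionnaires, the walk test and the CT.

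The primary outcome is PSQI (Protocol XVIII). The SAP states: "The Wilcoxon rank-sum test will be used to compare changes in PSQI, CAT, and the 6-minute walk test from enrollment to the 6-week visit", comparing the intervention group with the control group.

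**The concern.** Sealed envelopes conceal the allocation until they are opened and do nothing afterwards. With usual care as comparator and no masking described, participants and staff probably know the arm when baseline is recorded, although the documents do not say so. PSQI, CAT and the other questionnaires are self-reported, and the 6-minute walk depends on effort. A participant who has just been assigned the device, or has just learned that there will be none, may answer or walk differently.

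Randomisation makes the arms comparable in expectation only for what is measured before the arm can have an influence. Here half of each change score is recorded after that point. The result could be a false benefit or a hidden real one.

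Two further consequences follow from the order:

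- Inability to do the walk or the CT is an exclusion criterion (Protocol X), but both are first performed in the study after randomisation.
- Pregnancy is also an exclusion. The only stated timing for its test is "Before beginning the CT and MRI scans, the urine pregnancy test for females of childbearing potential will be checked", and the CT follows randomisation. A withdrawal after randomisation is therefore possible.

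**Working it through.** **The plan's own figure.** Inputs from Protocol XVIII: PSQI mean 9.3, SD 3.8, target below 5, 80% power, two-sided 5%, ratio 2:1, stated total 27. Taking the effect as 9.3 − 5 = 4.3:

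- Control-arm n = (1 + 1/2) × (1.960 + 0.842)² × 3.8² / 4.3² = 1.5 × 7.849 × 0.781 = 9.19.
- Total = 3 × 9.19 = 27.6, which reproduces the stated 27 to rounding.
- At 18:9, power is 79.2% (normal approximation) or 75.9% (t-test).

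The order of procedures does not change this sample size. It is used below as the setting for the illustration.

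**How a baseline shift enters the analysis.** Let b be the amount by which knowing the arm raises reported baseline PSQI in the HHHFA arm relative to usual care.

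- Difference in change = (difference at week 6) − (difference at baseline), so the bias is −b. Lower PSQI is better, so b > 0 looks like benefit and b < 0 hides it.
- With baseline as a covariate and equal SDs at both visits, the slope is about r (the baseline/follow-up correlation), so the bias is about −r × b. It is reduced but not removed. The protocol's mixed model names demographics and lung function as covariates, not baseline PSQI.

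**Assumptions not in the documents:** the values of b and r, normally distributed changes, and 3.8 as the SD at each visit.

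- SD of change = 3.8 × √(2(1 − r)).
- Standard error of the difference at 18:9 = SD of change × √(1/18 + 1/9) = SD of change × 0.408.

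| | r = 0.3 | r = 0.5 | r = 0.7 |
|---|---|---|---|
| SD of change | 4.50 | 3.80 | 2.94 |
| Standard error | 1.84 | 1.55 | 1.20 |
| Rank-sum type I error, b = 0.5 | 5.4% | 5.6% | 6.3% |
| Rank-sum type I error, b = 1 | 7.5% | 8.7% | 11.4% |
| Rank-sum type I error, b = 2 | 16.4% | 21.6% | 33.0% |
| t-test type I error, b = 1 | 8.2% | 9.5% | 12.6% |
| t-test type I error, b = 2 | 18.2% | 23.6% | 36.0% |
| Rank-sum power, effect 4.3, b = 0 | 57.6% | 72.1% | 90.9% |
| Rank-sum power, effect 4.3, b = −1 | 37.6% | 49.5% | 71.5% |
| Baseline-adjusted, b = 1: size of bias (points) | 0.31 | 0.51 | 0.70 |
| Baseline-adjusted, b = 1: type I error | 5.4% | 6.4% | 9.0% |

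The rank-sum rows come from simulation. The exact two-sided rank-sum test at 18:9 has an actual size of 4.6%, so that is the reference for its type I error. The t-test rows use the noncentral t distribution with 25 degrees of freedom and noncentrality b / standard error. The adjusted rows are simulated analyses of covariance.

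**Which measures are exposed.** Self-reported questionnaires are the most open to influence, then the 6-minute walk. CT is the least, because emphysema and gas trapping are defined by voxel thresholds; breath-hold effort and visual reading of mucus plugs remain open. Screening spirometry is not affected because it precedes randomisation, although the Design paragraph also lists spirometry among the baseline tests.

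**The case against.** The strongest reply is that the mechanism is inferred. Neither document says when the arm is disclosed, and the device is handed over at the end of the visit. That is fair, and it is why the bias is called possible. But the handover sentence concerns the device, not disclosure of the arm, and nothing in the plan withholds the arm until then.

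A second reply is that no document supports any particular shift. Two points is 2/3.8 = 0.53 SD and nearly half the planned effect, and at 0.5 points the type I error hardly moves. This stands: the harm is small if the shift is small, and the table should be read from its low end.

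Third, the supporting details are uneven. Table 1 cannot be a strict chronology, since it lists device training above the questionnaires while the text puts training last. The order it gives for demographics and medications is therefore weak evidence of a contradiction. The Design paragraph adds little beyond sentence order. The pregnancy test is a separate matter, since the plan sets only a latest time for it. These points narrow the case without touching the explicit statement in the Baseline visit paragraph.

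Fourth, this is a pilot, and week-6 PSQI is self-reported after known treatment in any case. That is true: reordering removes one avoidable source of reporting bias, not all of it.

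**Conclusion.** The concern holds. As written, the plan records the baseline of its primary outcome after randomisation with no stated protection against knowledge of the arm, and the SAP's contrast uses that baseline directly. No passage reverses the order.

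The size cannot be determined from the documents. Under the assumed correlations of 0.3 to 0.7, the effect on type I error runs from negligible at a 0.5-point shift to about 7.5–11.4% at 1 point and 16.4–33.0% at 2 points. A 1-point shift in the opposite direction costs roughly 19 to 23 percentage points of power for a 4.3-point effect (57.6 − 37.6 = 20.0; 72.1 − 49.5 = 22.6; 90.9 − 71.5 = 19.4). Baseline adjustment would lessen the bias, not cure it. Because the remedy is cheap, this should be fixed. Confidence that a material bias would arise in practice is only medium.

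**What to change.** At Visit 1, confirm eligibility on history and screening spirometry first, to limit needless CT. Then complete the pregnancy test, questionnaires, 6-minute walk and CT, make the final eligibility check, and only then open the envelope. Leave device training and handover after randomisation.

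Text changes:

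- **XI, opening paragraph:** say that the envelope is opened after the baseline measurements.
- **XI, Baseline visit:** place the measurements before randomisation.
- **I, Design paragraph:** put the baseline sentence ahead of the randomisation sentence, and say whether baseline spirometry is the screening spirometry.
- **XII, Urine Pregnancy Test:** state that the result is known before randomisation. This follows once the CT precedes it.
- **Table 1:** move the randomisation and device-training rows below Chest CT.

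The cost is wording and two table rows, with the same visit, procedures and staff. The downside is that a few people may have baseline tests, including CT, and then not be randomised.

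Protocol V4.0 is dated October 2020, and enrolment was estimated for June 2019 to June 2021, so recruitment may already have begun. If so, record which order each participant followed. If the arm was in practice withheld until baseline was complete, say so. A comparison of week-6 PSQI alone, which a baseline shift does not affect, could be added as a sensitivity analysis. At 18:9 and SD 3.8 it has 75.9% power by t-test for 4.3 points.

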This study will be conducted in compliance with the protocol, Good Clinical Practice and the applicable Food and Drug Administration and other Department of Health and Human Services regulatory requirements.

All key personnel (all individuals responsible for the design and conduct of this study) have completed Human Subjects Protection and Good Clinical Practice training.

IV. IRB Oversight

Human Subjects Office / IRB

J. [name]

[name]

[name]

[name]

FWA#: FWA00003007

Voice: [contact]

[contact]

Email: [contact]

V. Location of Study Procedures

University of Iowa
[name]
[name]

VI. Main Hypothesis

HHHFA during sleep in COPD patients with chronic bronchitis improves respiratory symptoms, sleep quality, lung function, and exercise capacity.

VII. Main Screening Criteria

We will recruit COPD men and non-pregnant women of any ethnic background with the age above 18 years with the following characteristics: post-bronchodilator FEV1%predicted below 70%, chronic bronchitis defined as cough with daily sputum production, and at least 1 exacerbations in the last year.

VIII. Recruitment procedures

The study team will utilize email blasts and University of Iowa Noon News advertising to recruit subjects for this study. We will also advertise study at the Iowa City VAMC. Upon study beginning and ensuring the smooth operation of the protocol, we will apply to the VA for permission to recruit subjects from the Iowa City VAMC. To avoid any coercion all subjects are offered the opportunity to talk with their primary care provider or family prior to signing a consent form. Study participation has no influence on their medical care.

IX. Inclusion Criteria

- COPD diagnosis by health care provider
- Smoking with at least 10 pack-years
- Post-bronchodilator FEV1/FVC <0.7
- Post-bronchodilator FEV1%predicted <70%
- Chronic bronchitis, defined as chronic cough with daily sputum production
- ≥1 COPD exacerbations within the last year

X. Exclusion Criteria

- Obstructive sleep apnea or suspected obstructive sleep apnea that requires positive airway pressure treatment
- Patients that use oxygen supplementation continuously (patients that use oxygen supplementation only at exertion, as needed, or at night will NOT be excluded)
- Any planned procedure that makes ineligible according the PI clinical judgement
- Unable to perform a spirometry, 6-minute walk test or chest CT

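### The first walk test and chest CT follow randomisation and the pregnancy test has no stated place relative to it, so a patient can be found ineligible after allocation, with no rule for the analysis

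*Protocol*

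**What the plan says.** Protocol Section X (Exclusion Criteria) lists pregnancy and also "Unable to perform a spirometry, 6-minute walk test or chest CT".

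Section XI (Schedule of events) opens with the screening step: "After obtaining informed consent, participants will perform a screening pre-bronchodilator and post-bronchodilator spirometry". It continues: "Participants who meet eligibility criteria will be randomized (2:1) to receive either HHHFA or usual care for 6 weeks". The allocation method is given as "Randomization will be performed using sealed envelopes".

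The baseline visit is described next: "After randomization, participants will have baseline measurements and training in the device". History and questionnaires come first. Then: "Subsequently, participants will perform a 6-minute walk test follow by an inspiratory and expiratory chest CT". Table 1 puts all of this at Visit 1 and lists the walk test and chest CT below the randomisation row.

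Section XII, under Urine Pregnancy Test, says: "Before beginning the CT and MRI scans, the urine pregnancy test for females of childbearing potential will be checked". The consequence is "If the result is positive for pregnancy subject will be withdrawn". Table 1 has no row for this test.

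The comparator is usual care, and neither document describes blinding. Neither defines an analysis population. The SAP compares changes from enrolment to week 6 with a Wilcoxon rank-sum test and does not mention patients withdrawn after allocation.

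**The concern.** Eligibility should be settled before the envelope is opened. If a criterion is checked afterwards, a randomised patient can turn out not to qualify, and someone must then decide whether to keep that patient.

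A urine pregnancy result leaves no room for judgement. Whether a patient is unable to do a walk test or a breath-hold CT does. If that judgement is made with the arm known, removals can differ by arm, and the groups compared are no longer the groups randomised. More recruitment would not correct this. Each removal would also use part of an attrition allowance of only three patients.

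**Working it through.** **Step 1. Set the passages side by side.**

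| Exclusion criterion (Section X) | Where it is tested | Position relative to randomisation | Stated consequence of failure |
|---|---|---|---|
| Unable to do spirometry | Section XI, screening | Before | Not randomised |
| Unable to do 6-minute walk | Section XI, baseline visit; Table 1 | After | None stated |
| Unable to do chest CT | Section XI, baseline visit; Table 1 | After | None stated |
| Pregnancy | Section XII, tied to the scans | Not stated | Withdrawal |

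The order of the walk and CT looks deliberate, because Section XI asks for the 6-week visit to repeat the baseline sequence. The place of history-taking is unclear: the Section XI text puts it after randomisation, while Table 1 lists it above the randomisation row.

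**Step 2. Reproduce the plan's sample size, to see what margin exists.** Inputs from Section XVIII: PSQI mean 9.3, SD 3.8, target 5, two-sided 5%, power 80%, ratio 2:1. The difference 9.3 − 5 = 4.3 is an assumption, since only the target is given.

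Total = 3 × 1.5 × [3.8 × (1.960 + 0.842) / 4.3]² = 27.6 unrounded, against the stated 27. At 18:9 the normal-approximation power is 79.2%. The stated figure is reproduced to rounding. The goal of 30 leaves 30 − 27 = 3 patients.

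**Step 3. Show what removals would do.** The number removed is an assumption, because the documents give no rate. SE = 3.8 × √(1/n₁ + 1/n₂).

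| HHHFA : usual care | SE | Power, normal approximation | Power, t-test |
|---|---|---|---|
| 20:10, none removed | 1.47 | 83.2% | 80.5% |
| 19:10, one HHHFA removed | 1.48 | 82.5% | 79.7% |
| 20:9, one usual-care removed | 1.53 | 80.5% | 77.6% |
| 17:10, three HHHFA removed | 1.51 | 81.0% | 77.9% |
| 20:7, three usual-care removed | 1.67 | 73.1% | 69.7% |

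One usual-care removal raises the SE by a factor of 1.53/1.47, or 3.6% before rounding.

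**Step 4. Show a possible shift in the arm mean.** If the removed patient lay 1 SD from the mean of the original arm, the mean of those left moves by 3.8/9 = 0.42 points in usual care, or 3.8/19 = 0.20 points in HHHFA. Against 4.3 points these are about 10% and 5%. Both assume a single removal at that distance; they do not estimate the bias in this trial.

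**The case against.** The best reply is that the protocol randomises only participants who meet the eligibility criteria. It seeks non-pregnant women, says that subjects are pre-screened and screened, and Table 1 lists screening, history and a physical examination above randomisation. Inability to do a walk or CT can be judged from history and examination. A short walk is a result rather than a failure, and the breath-holds last only 5 to 10 seconds. The pregnancy test would satisfy its own wording if done at screening, and that wording may also cover the 6-week CT, where a positive result is not a baseline eligibility failure. Withdrawal is stated for pregnancy alone.

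Most of this stands. A reader might infer that ineligible patients are allocated and then removed with the arm known. The documents do not support that as a description of the procedure. For the walk and CT no removal rule exists, and knowledge of the arm is a fair inference from an unblinded usual-care comparator but is not stated.

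The reply does not remove the gap. The eligibility sentence gives an intention, with no step that settles these criteria first, and the stated sequence puts the first walk and CT attempts after allocation. A check based on history cannot be relied on while the text and Table 1 disagree about when history is taken. The silence on analysis is also unaffected. The illustration in Step 4 for usual care is the less favourable case; at 2:1 a single removal is more likely to come from HHHFA, where the shift is half as large.

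**Conclusion.** The point holds as a weakness in sequence and in the analysis rule. The plan allows a patient to be found ineligible after allocation, with no blinding described, and does not say how that patient is analysed.

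Its frequency and effect cannot be computed from the documents. Positive pregnancy tests are likely to be rare in this population, so failed walk or CT attempts are the likelier route. The firm figure is the three-patient allowance on which such losses would draw. The power and mean-shift figures rest on an assumed 4.3-point difference, SD 3.8, a 20:10 split and hypothetical removals; any dropout would produce the same loss of power. A reader should not take them as evidence of actual bias. The change is worth making because it guards against arm-dependent exclusion at little cost.

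**What to change.** 1. In Section XI and Table 1, place the first 6-minute walk and chest CT between screening spirometry and opening the envelope, at the same visit.
2. Reconcile the eligibility and baseline-visit text of Section XI, the pregnancy-test text of Section XII and Table 1, so that every baseline exclusion criterion, including pregnancy status, is settled before randomisation. Give the pregnancy test its own row in Table 1.
3. In Section XVIII and the SAP, define the primary analysis set. State that a randomised patient who later cannot do a walk test or CT keeps PSQI follow-up and stays in the primary comparison as randomised. Say how any patient withdrawn after allocation is handled in the analysis.

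The cost is a re-ordering within one visit, edits to the table and text, and a few patients who are tested, including by CT, and then not randomised. The sample sizes of 27 and 30 do not change, since these failures become screen failures. The same re-ordering, extended to the questionnaires, would also deal with the separate matter of baseline scores taken after allocation.
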